8.3 Inclusion Criteria

Candidates for this study must meet ALL of the following inclusion criteria:

PAD Positive Cohort

- Subject meets PAD positive criteria set forth in Section 8.3
- Subject is willing and able to provide an informed consent.
- Subject is willing and able to comply with the study procedures.
- Subject is able to understand the study procedures.
- Subject is scheduled for vascular examination that includes noninvasive assessments as standard of care: ABI, TBI, and either a Duplex ultrasound or Angiogram.

Healthy Cohort

- Subject is willing and able to provide an informed consent.
- Subject is willing and able to comply with the study procedures.
- Subject is able to understand the study procedures.
- Subject has no history of positive PAD diagnosis and is not currently suspected of having PAD.

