3.2 Purpose

The purpose of the investigation is to assess the efficacy of the FlowMet-R device in diagnosing PAD and CLI in patients scheduled for peripheral vascular examination. The results of the assessment of the FlowMet-R device will be compared to gold standard diagnostics including ABI, TBI, and Doppler Ultrasound.

4. Objectives and/or Endpoints

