This study has many clinical implications. FlowMet-R is the first noninvasive technology to provide accurate and continuous quantification of microvascular perfusion. Hence, this technology may provide improved diagnostic and/or prognostic capabilities during procedures and in outpatient settings. The current study will set the foundation for future indications of FlowMet-R technology in vascular care.

The purpose of the investigation is to assess the efficacy of the FlowMet-R device in diagnosing PAD and CLI in patients scheduled for peripheral vascular examination. The results of the assessment of the FlowMet-R device will be compared to gold standard diagnostics including ABI, Toe Brachial Index (TBI), and Doppler Ultrasound.

4. Study Objectives

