5.3 Study Population

Subjects shall be enrolled until the following number of limbs have been measured:

- 160 control limbs (no diagnosed PAD)
- 240 limbs with PAD
 - Of the limbs with PAD, a subset >100 limbs with CLI
 - Of the limbs with PAD, a subset >54 limbs without CLI

Any patient being seen for diagnosis of suspected PAD may be screened for enrollment in the PAD cohort. For patients undergoing intervention, supplemental data will be taken within a catheterization laboratory. Control data from a healthy cohort will also be gathered. Recruitment of healthy subjects is at the site's discretion. Third party recruitment services such as researchmatch.org may be used.

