5.5 Inclusion Criteria

Candidates for this study must meet all of the following inclusion criteria:

PAD Positive Cohort

- Subject meets PAD positive criteria set forth in Section 4.1.1.1
- Subject is willing and able to provide an informed consent.
- Subject is willing and able to comply with the study procedures.
- Subject is able to understand the study procedures.
- Subject is scheduled for vascular examination that includes noninvasive assessments as standard of care: ABI, TBI, and either a Duplex ultrasound or Angiogram.

Healthy Cohort

- Subject is willing and able to provide an informed consent.
- Subject is willing and able to comply with the study procedures.
- Subject is able to understand the study procedures.
- Subject has no history of positive PAD diagnosis and is not currently suspected of having PAD.

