5.6 Exclusion Criteria

Candidates for this study who meet any of the following criteria at the time of the baseline visit are not eligible to be enrolled in this study:

PAD Positive Cohort Exclusion

- Subject is under 40 or unable to consent.
- Subject has any medical condition, which, in the judgment of the Investigator and/or designee, makes the subject a poor candidate for the investigational study.
- Subject is excluded from analysis if no stenosis is found during Doppler but Tibial disease is suspected and Tibial ultrasound is not able to be performed.
- Subject does not have a suitable finger to attach the FlowMet-R probe.
- Subject does not have a suitable 1st or 2nd digit to attach FlowMet-R probe on the limb of interest.
- Subject has undergone revascularization within the last 90 days
- Subject cannot lay safely in a supine position.

Healthy Cohort Exclusion

- Subject is under 40 or unable to consent.
- Subject has any medical condition, which, in the judgment of the Investigator and/or designee, makes the subject a poor candidate for the investigational study.
- One or more limbs has a prior or current diagnosis of PAD, or is reasonably suspected of having a diagnosis of PAD.
- Subject does not have a suitable finger to attach the FlowMet-R probe.
- Subject does not have a suitable 1st or 2nd digit to attach FlowMet-R probe.
- Subject has undergone revascularization within the last 90 days

6. Determination of Sample Size

The rate of PAD and CLI within the population seen at a typical vascular clinic is estimated from a prior investigation. In that study, 100 limbs were assessed using the ABI and graded using the Rutherford classification scheme. PAD (diagnosed via ABI score of <0.9) was present in 63% of limbs. CLI (estimated as having a Rutherford category of ≥ 4) occurred in 15% of limbs. FlowMet-R data was also collected from the above limbs, and the data analysis techniques used in the data analysis section below were applied to build a diagnostic model for PAD and CLI. ROC curves were then generated for the diagnosis of both Claudication and CLI. The resulting area under the curve (AUC) for these ROC curves was 0.67 and 0.80, respectively. However, the Claudicant group AUC had a tighter confidence interval due to larger sample size (84 vs. 22, respectively).

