7.10 Evaluation of Objectives

7.10.1 Primary Objectives

The primary objectives will compare the 95% CI of the AUC from the ROC curve to a value of 0.5 at 0-, 3-, and 6-months for the two definitions of PAD and one definition of CLI using the acceleration time from the FlowMet-R device. The 95% CI will not be corrected for repeated measures within a participant. If the 95% CI of the AUC excludes 0.5 at all time points for PAD or CLI, the acceleration time from the FlowMet-R device will be considered predictive of the respective endpoint. The 95% CI of the AUC will be derived using the method described in DeLong, et al (1998) [15]. Note, the definition of PAD will be defined two ways and analyzed separately. Definitions of PAD and CLI are provided in Section 4.1.1.1.1.

Three supplementary summaries will be computed. The sensitivity and specificity will be computed by selecting the point on the ROC curve closest to the upper left corner. Accuracy will be computed as the number of limbs correctly diagnosed divided by the total number of limbs.

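### The baseline PAD curve mainly contrasts PAD-positive entrants with unsuspected volunteers, so its accuracy figures are likely optimistic for patients scheduled for vascular examination

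*Protocol*

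**What the plan says.** Protocol 3.2 sets out to "assess the efficacy of the FlowMet-R device in diagnosing PAD and CLI in patients scheduled for peripheral vascular examination"; the SAP introduction repeats this.

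- **PAD cohort.** Protocol 8.3 requires every inclusion criterion to be met, and the first is "Subject meets PAD positive criteria set forth in Section 8.3". That pointer refers to its own section. The synopsis points to 8.4, which holds the exclusion criteria. SAP 5.5 has "Subject meets PAD positive criteria set forth in Section 4.1.1.1", and subsection 4.1.1.1.1 there contains the ABI, TBI and symptom definitions that SAP 7.10.1 uses as the reference standard for the ROC curves.
- **Healthy cohort.** Entry requires "Subject has no history of positive PAD diagnosis and is not currently suspected of having PAD" (SAP 5.5, same rule in Protocol 8.3). Recruitment may go through other departments, the community or a recruitment service (Protocol synopsis and 8.1). These subjects are measured once (Protocol 5; SAP 5).
- **Screening.** "Any patient being seen for diagnosis of suspected PAD may be screened for enrollment in the PAD cohort" (SAP 5.3).
- **Clinic patients who prove negative.** Protocol 4.1.1.1.1 counts PAD-cohort patients who do not meet the definition as PAD negative, outside the healthy cohort. Protocol 9.7.3 foresees enrolled patients whose ABI and TBI do not show PAD. SAP 7.12 classifies everyone by definition, whatever the enrolment cohort.
- **Conclusion rule.** Under SAP 7.10.1, if the 95% CI of the AUC excludes 0.5 at all time points, "the acceleration time from the FlowMet-R device will be considered predictive of the respective endpoint".

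**The concern.** A diagnostic test used in a vascular clinic has to separate patients with PAD from patients who were sent for examination, often with symptoms or risk factors, and turn out not to have it. The plan sets no number for that second group. Its planned negatives, 160 limbs, come from people nobody suspects of PAD, which is probably an easier contrast.

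A baseline AUC, sensitivity, specificity or accuracy from this mixture could be read as performance in scheduled patients, because the purpose is worded that way and neither document restricts the interpretation.

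**Working it through.** **Which limbs enter the baseline PAD curve**

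1. Positives: limbs meeting SAP 4.1.1.1.1, nearly all from the PAD cohort; 240 are planned.
2. Negatives: 160 planned volunteer limbs, plus an unplanned number of PAD-cohort limbs that do not meet the definition. The latter can be subjects who improved or were wrongly screened, and possibly opposite limbs.
3. At 3 and 6 months no volunteer has a visit, so all negatives are PAD-cohort limbs. The baseline curve and the follow-up curves use different negatives.
4. For CLI, the negatives at planned numbers are 240 − 100 = 140 PAD limbs without CLI plus 160 volunteer limbs. Volunteers are 160/300 = 53% of them, so the CLI contrast is less affected.

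**How large the optimism could be (illustration only)**

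The plan gives no figure to reproduce here. Its only AUCs are the pilot values in SAP 6, 0.67 (claudication) and 0.80 (CLI), which the sample-size argument carries over to PAD groups against healthy controls. I use them as two starting values for an AUC against volunteers; the documents do not say what the pilot's negatives were.

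Assume an equal-variance binormal model in which suspected but negative limbs lie a fraction f of the way from volunteers to PAD. Then AUC(clinic) = Φ[(1 − f) × Φ⁻¹(AUC(volunteers))], with Φ⁻¹(0.67) = 0.440 and Φ⁻¹(0.80) = 0.842.

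| AUC against volunteers | f = 0.10 | f = 0.25 | f = 0.50 |
|---|---|---|---|
| 0.67 | 0.654 | 0.629 | 0.587 |
| 0.80 | 0.776 | 0.736 | 0.663 |

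A few clinic negatives in the pooled curve correct little of this. With f = 0.50 and a starting AUC of 0.67, if 10% of the negatives are such limbs the pooled AUC is 0.9 × 0.67 + 0.1 × 0.587 = 0.662. At 25% it is 0.75 × 0.67 + 0.25 × 0.587 = 0.649. Both stay well above 0.587.

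**What a clinic-only curve could show**

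The number of clinic negatives, n₀, is not planned, so I show a range. The Hanley-McNeil variance is [A(1 − A) + (n₁ − 1)(Q₁ − A²) + (n₀ − 1)(Q₂ − A²)]/(n₁n₀), with Q₁ = A/(2 − A) and Q₂ = 2A²/(1 + A). Put in A = 0.67 and n₁ = 240, so Q₁ − A² = 0.0549 and Q₂ − A² = 0.0887, and treat limbs as independent.

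| n₀ | SE | 95% half-width (1.96 × SE) |
|---|---|---|
| 160 (planned volunteers, for comparison) | 0.0267 | 0.052 |
| 80 | 0.0325 | 0.064 |
| 40 | 0.0418 | 0.082 |
| 20 | 0.0559 | 0.110 |

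The clinic-only curve would be less precise but still informative at moderate n₀, which is why n₀ has to be reported with it.

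**The case against.** The case for the plan has real force, and it rules out several stronger readings that a reader might infer.

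- **That a positive trial result would show only separation from volunteers.** The documents do not support this. The conclusion rule needs all time points, and volunteers contribute only at baseline. The point is confined to the baseline curve.
- **That every suspected but negative clinic patient is screened out.** This is not established. Signing consent counts as enrolment (Protocol 8.2), FlowMet-R is measured before the noninvasive tests (Protocol 9.6), and Protocol 4.1.1.1.1 and 9.7.3 with SAP 7.1.3 and 7.12 keep such patients in the analysis as negatives. What stands is that the inclusion criterion pulls the other way and that no number of them is planned.
- **That the entry rule removes 37% of the intended population.** The pilot statement is "PAD (diagnosed via ABI score of <0.9) was present in 63% of limbs" (SAP 6). The remaining 100 − 63 = 37% is per limb and by ABI alone. The trial's definition adds ABI above 1.4, TBI verification and postexercise ABI, and some of those limbs may be opposite limbs of PAD patients. The share of suspected but negative patients is not in the documents.
- **That the AUC would fall by the amounts tabulated.** The fraction f is free; the table shows direction and a possible range.

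It can also be said that the contrast is disclosed: SAP 6 frames the sample size as PAD groups against healthy controls, and SAP 7.2 calls the results descriptive. That supports keeping the design. It does not supply the missing limit on interpretation, since the purpose still names scheduled patients.

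**Conclusion.** The point holds for the baseline PAD curve. Its AUC, sensitivity, specificity and accuracy mainly describe separation of PAD limbs from limbs of unsuspected volunteers, and are likely optimistic for diagnosis in patients scheduled for examination.

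The direction rests on one assumption: that suspected patients who prove negative resemble PAD patients more than volunteers do on acceleration time. The link between entry and the reference standard rests on SAP 5.5, because the Protocol's own pointers do not lead to a definition. The size cannot be derived from the documents. The effect is weaker for CLI, and the 3- and 6-month curves raise a different matter, since their negatives are all PAD-cohort limbs.

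**What to change.** In SAP 7.10.1:

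1. Report, beside the pooled baseline PAD curve, a baseline ROC curve restricted to PAD-cohort limbs classified by 4.1.1.1.1. Give its CI and the number and source of its negatives (opposite limbs, or subjects not meeting the definition). It also matches the population of the 3- and 6-month curves.
2. State that the pooled baseline curve supports only separation of PAD limbs from limbs of unsuspected volunteers. State also that accuracy among suspected but PAD-negative clinic patients is not established unless enough such patients are in the clinic-only curve. Opposite limbs of PAD patients do not answer that question.
3. Reconcile the pointers for the PAD-positive criteria (Protocol synopsis and 9.7.3 to 8.4, Protocol 8.3 to itself, SAP 5.5 to 4.1.1.1) with Protocol 4.1.1.1.1 and 9.7.3 and SAP 7.12.

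The cost is some wording and one extra curve from data already planned for collection. That curve is likely to be lower and less precise, and the claim becomes narrower.

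Dropping the PAD-positive entry criterion is not part of this fix. It is a design trade-off against the limb quotas: at the pilot rate of 15%, 100 CLI limbs would take about 100/0.15 = 667 consecutive clinic limbs.

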8.4 Exclusion Criteria

Candidates for this study who meet any of the following criteria at the time of the baseline visit are NOT eligible to be enrolled in this study:

PAD Positive Cohort Exclusion

- Subject is under 40 or unable to consent.
- Subject has any medical condition, which, in the judgment of the Investigator and/or designee, makes the subject a poor candidate for the investigational study.
- Subject is excluded from analysis if no stenosis is found during Doppler but Tibial disease is suspected and Tibial ultrasound is not able to be performed.
- Subject does not have a suitable finger to attach the FlowMet-R probe.
- Subject does not have a suitable 1st or 2nd digit to attach FlowMet-R probe on the limb of interest.
- Subject has undergone revascularization within the last 90 days

- Subject cannot lay safely in a supine position.

Healthy Cohort Exclusion

- Subject is under 40 or unable to consent.
- Subject has any medical condition, which, in the judgment of the Investigator and/or designee, makes the subject a poor candidate for the investigational study.
- One or more limbs has a prior or current diagnosis of PAD, or is reasonably suspected of having a diagnosis of PAD.
- Subject does not have a suitable finger to attach the FlowMet-R probe.
- Subject does not have a suitable 1st or 2nd digit to attach FlowMet-R probe.
- Subject has undergone revascularization within the last 90 days

9. Study Procedures

9.1 Schedule of Events

Patients will follow the below event schedules based on their cohort. PAD patients will follow Event Schedule A, Registry patients will follow Event Schedule B, and the Healthy Cohort subjects will follow Event Schedule C.

[figure not shown]
Initial and Follow-Up Visits: Event Schedule A

FlowMet-R Blood Flow Measurement for PAD and CLI Clinical Investigation Plan

[figure not shown]
Version 3.1

Page 20 of 42

[figure not shown]
Form
Medtronic

Interventional Procedure: Event Schedule B

Healthy Cohort Single Visit: Event Schedule C

9.2 Data Collection

Data collection requirements are summarized in Table 2 below.

Table 2: Data collection and study procedure requirements at subject visits

Study Procedure	Baseline	Registry Entry (if applicable)	3 month	6 month	Study Exit
Informed Consent	X				
Inclusion/exclusion assessment	X				
Medical History/Demographics	X		X	X	
Rutherford Grade	X		X	X	
QoL Survey	X		X	X	
FlowMet Collection	X		X	X	
FlowMet Collection Intraprocedure		X			
ABI/TBI	X		X	X	
Exit subject					X
AEs	As they occur				
Study deviations	As they occur				

9.3 Scheduled Follow-up Visit Windows

The target dates and windows for each visit are detailed in the table below. Should a subject miss a visit or the visit fall outside the pre-specified window, a study deviation must be reported and the original follow-up schedule maintained for subsequent visits.

Data analyses include follow-up visits regardless of whether the visit occurs within the window. Therefore, a late visit is preferred over a missed visit, but must be accompanied by a deviation report. Follow-up visit windows are listed in Table 3, and are based on days post-FlowMet-R assessment.

Table 3: Data collection and study procedure requirements at subject visits

Study Follow-up Visit	Window (Calculated days post-FlowMet-R Assessment)		
	Window Start	Target	Window End
Follow-up Visit 1	2 months	3 months	4 months
Follow-up Visit 2	5 months	6 months	7 months

9.4 Subject Consent

Informed consent is defined as a legally effective documented confirmation of a subject's voluntary agreement to participate in a particular study. This process includes obtaining an Informed Consent Form that has been approved by the study site's IRB and signed and dated by the subject. A subject may only consent after information has been given and explained to the subject on all aspects of the clinical investigation that are relevant to the subject's decision to participate.

Prior to enrolling subjects, the informed consent must be approved by the site's IRB. The document must be controlled to ensure it is clear which version was approved by the IRB. Any adaptation of the sample informed consent must be reviewed and approved by Medtronic and the IRB reviewing the application prior to enrolling subjects.

The investigator must notify the subject of any significant new findings about the study that become available during the course of the study which are pertinent to the safety and well-being of the subject, as this could impact a subject's willingness to participate in the study. If relevant, consent may be requested from subjects to confirm their continued participation.

Prior to initiation of any study-specific procedures, informed consent must be obtained from the subject. The informed consent process must be conducted by the principal investigator or an authorized designee, and the informed consent form must be given to the subject in a language he/she is able to read and understand. The process of informed consent must be conducted without using coercion or undue improper influence on or inducement of the subject to participate by the investigator or other study site personnel. The informed consent process shall not waive or appear to waive subject's legal right. The language used shall be as non-technical as possible and must be understandable to the subject and the impartial witness, where applicable.

The subject must have ample time and opportunity to read and understand the informed consent form, to inquire about details of the study, and to decide whether or not to participate in the study. All questions about the study should be answered to the satisfaction of the subject.

When the subject decides to participate in the study, the informed consent must be signed and personally dated by the subject and investigator or authorized designee, as required by the informed consent, and ensured by the principal investigator or his/her authorized designee.

A copy of the informed consent, signed and dated as required by law, must be provided to the subject. If the informed consent is obtained the same day the subject begins participating in study-related procedures, it must be documented in the subject's case history that consent was obtained prior to participation in any study-related procedures.

In the event that the subject cannot read and/or write, the informed consent process shall be obtained through a supervised oral process. An independent and impartial witness must be present during this process. This informed consent and any other information must be read aloud to the prospective subject. Whenever possible, the subject shall sign and personally date the informed consent form. The witness signs and personally dates the informed consent attesting that the information was accurately explained and that informed consent was freely given.

The original signed informed consent must be filed in the hospital/clinical chart and/or with the subject's study documents. The informed consent must be available for monitoring and auditing.

9.5 Baseline Visit

9.5.1 Relevant Medical History and Demographics

The clinician will document demographics and medical history on the associated Case Report Forms and enter them into the Electronic Data Capture (EDC) system.

For patients that are seen for a vascular (re)intervention and are part of the registry portion of the study, standard information about the patient's scheduled intervention, treatment plan, and follow up schedule will be contained in the record log and uploaded as a digital copy.

9.5.2 QoL Assessment

Quality of Life (QoL) assessments are an important reporting standard for PAD patients. The VascuQoL is a questionnaire that has been used frequently by clinical studies in the past in evaluating QoL in CLI and Claudication patients [28]. Here, we choose to use the abbreviated VascuQoL-6, a 6 item survey that has been shown to be as effective as the standard VascuQoL, but with reduced time burden on patients and clinicians [29].

9.5.3 Rutherford Classification / Visual Assessment

[figure not shown]
The Rutherford scoring system is commonly used in vascular assessment of PAD patients. Grade and category will both be recorded for enrolled patients on the CRF. The clinician will also note visual inspection of limbs for evidence of ulcers or wounds. If present, wound grade and foot infection grade will be noted as well as wound healing trajectory.

